8.1.3. Clinical Evaluation

8.1.3.1. Clinical Signs and Symptom Scores, Clinical Outcomes, and Clinical Response

Clinical signs and symptoms of acute cystitis will be recorded based on participant interview per the SoA (Section 1.3) using the scoring system and instructions in 10.10. At Baseline, the participant must present with at least 2 signs and symptoms and have a total cumulative symptom score ≥ 2 . At TOC, success is defined as normal presentation of signs and symptoms with a total cumulative symptom score of zero and no new signs and symptoms of the infection under study.

A study physician or otherwise appropriately medically trained staff will determine the individual clinical signs and symptoms scores for acute cystitis (10.10) at the On-therapy, TOC, and Follow up Visits. The same scorer will be used at all assessment time points for each participant, on all occasions, whenever possible. The score will be used to programmatically determine the clinical outcome at the On-therapy Visit (Table 11) and the clinical outcome and response (success or failure) at the TOC Visit (Table 12) and the Follow-up Visit (Table 13).

Table 11 Clinical Outcome at the On-Therapy Visit

Defining Criteria	Outcome ^a
Resolution of signs and symptoms of acute cystitis present at Baseline (and no new signs and symptoms), without the participant receiving other systemic antimicrobials before the On-therapy Visit	Clinical resolution
Improvement in total symptom scores from Baseline, but not complete resolution, without the participant receiving other systemic antimicrobials before the On-therapy Visit	Clinical improvement
Worsening or no change in total symptom scores from Baseline or the participant received other systemic antimicrobials for the current infection prior to or on the date of the On-therapy Visit	Clinical worsening
The Baseline score is missing, or The On-therapy assessment is missing, or The participant received other systemic antimicrobials not for the current infection prior to the assessment (unless clinical worsening outcome criteria were met)	Unable to determine

a. A study physician or otherwise appropriately medically trained staff will determine the individual clinical signs and symptoms scores for acute cystitis (10.10), which will then be used to programmatically determine the clinical outcome. The same scorer will be used at all assessment time points for each participant, on all occasions, whenever possible.

Table 12 Clinical Outcome and Response at the Test-of-Cure Visit

Defining Criteria	Outcome ^a	Response
Resolution of signs and symptoms of acute cystitis present at Baseline (and no new signs or symptoms), without the participant receiving other systemic antimicrobials before the TOC Visit	Clinical resolution	Clinical success
Improvement in total symptom scores from Baseline, but not complete resolution, without the participant receiving other systemic antimicrobials before the TOC Visit	Clinical improvement	Clinical failure
Worsening or no change in total symptom scores from Baseline or the participant received other systemic antimicrobials for the current infection before or on the date of the TOC Visit	Clinical worsening	Clinical failure
The Baseline score is missing, or The TOC assessment is missing, or The participant received other systemic antimicrobials not for the current infection prior to the assessment (unless clinical worsening criteria were met)	Unable to determine	Clinical failure

TOC = Test-of-Cure

a. A study physician or otherwise appropriately medically trained staff will determine the individual clinical signs and symptoms scores for acute cystitis (10.10), which will then be used to programmatically determine the clinical outcome. The same scorer will be used at all assessment time points for each participant, on all occasions, whenever possible.

Table 13 Clinical Outcome and Response at the Follow-up Visit

Defining Criteria	Outcome ^a	Response
Resolution of signs and symptoms of acute cystitis demonstrated at the TOC Visit persist at the Follow-up Visit (and no new signs and symptoms), without the participant receiving other systemic antimicrobials before the Follow-up Visit	Sustained clinical resolution	Clinical success
Resolution of signs and symptoms of acute cystitis present at Baseline (and no new signs or symptoms), after clinical failure at TOC, without the participant receiving other systemic antimicrobials before the Follow-up Visit	Delayed clinical resolution	Clinical failure
Improvement in total symptom scores from Baseline, but not complete resolution, without the participant receiving other systemic antimicrobials before the Follow-up Visit	Clinical improvement	Clinical failure
Worsening or no change in total symptom scores at Follow-up compared to Baseline after clinical failure at TOC, or the participant received other systemic antimicrobials for the current infection before or on the date of the Follow-up Visit	Clinical worsening	Clinical failure
Signs and symptoms of acute cystitis reoccur at the Follow-up Visit after clinical success at TOC	Clinical recurrence	Clinical failure
1) The Baseline score is missing, or 2) The Follow-up assessment is missing, or 3) The participant received other systemic antimicrobials not for the current infection prior to the assessment (unless the clinical worsening or recurrence outcome criteria were met)	Unable to determine	Clinical failure

TOC = Test-of-Cure

a. A study physician or otherwise appropriately medically trained staff will determine the individual clinical signs and symptoms scores for acute cystitis (10.10), which will then be used to programmatically determine the clinical outcome. The same scorer will be used at all assessment time points for each participant, on all occasions, whenever possible.

8.1.3.2. Investigator Assessment of Clinical Response

The clinical signs and symptoms score will be determined for the primary endpoint, as described in Section 8.1.3.1 and 10.10. In addition, for secondary and exploratory purposes, a separate assessment of clinical response will be performed at the TOC and Follow-up Visits, or at the time of early withdrawal (Section 1.3). The investigator will assess the clinical response (clinical success, clinical failure, or indeterminate) for each participant based on the definitions in Section 10.11 and will document the response and reason(s) for clinical failure or indeterminate response, if applicable, in the eCRF. This assessment should be completed after the clinical signs and symptoms score is determined by the same study physician or otherwise appropriately medically trained staff who performed the clinical scoring assessment (Section 8.1.3.1 and 10.10).

8.2. Safety Assessments

Planned timepoints for all safety assessments are provided in the SoA (Section 1.3).

8.2.1. Physical Examinations

- A physical examination will be performed at the timepoints indicated in the SoA (Section 1.3) as follows:
 - At Baseline, the examination will include assessments of the respiratory, CV, abdominal, gastrointestinal, neurological, and urogenital systems. Height and weight will also be measured and recorded at the Baseline Visit (before dosing).
 - At the TOC Visits, the physical examination may be symptom directed and is only required if indicated for a specific participant.
- Investigators should pay special attention to clinical signs related to previous serious illnesses.
- Clinically significant changes from baseline or clinically significant new clinical signs will be reported as AEs.

8.2.2. Vital Signs

- Vital signs will be measured at the time points indicated in the SoA (Section 1.3).
- Vital signs will be measured in a semi-supine position after 5 minutes rest and will include temperature, systolic and diastolic blood pressure, and pulse rate.
- Vital sign measurements should be obtained before any blood draws scheduled on the same assessment day.
- Clinically significant changes from baseline will be reported as AEs.

8.2.3. Electrocardiograms

- Tripricate 12-lead ECGs (over an approximate 5- to 10-minute period) will be obtained as outlined in the SoA (see Section 1.3) using an ECG machine that automatically calculates the heart rate and measures PR, QRS, QT, and QTc

intervals. Refer to Section 7.1.2 for QTc withdrawal criteria and additional QTc readings that may be necessary.

- Ideally, ECGs will be obtained before any vital sign measurements or blood draws scheduled on the same assessment day; however, sites may perform procedures in an order per their standard of care, as long as participants return to a resting state prior to the start of the ECG collections.
- If any additional ECGs are performed during the study (if deemed necessary by the investigator), those may be collected as a single ECG; however, if that initial single reading shows QTc prolongation, then triplicate ECGs should also be performed (see Section 7.1.2).
- If clinically significant changes occur during the study, they will be reported as AEs.
- Electrocardiograms will be reviewed locally by the investigator for safety purposes.

8.2.4. Clinical Safety Laboratory Tests

- See 10.2 for the list of clinical laboratory tests to be performed and the SoA (Section 1.3) for the timing and frequency.
- The investigator must review the laboratory report, document this review, and record any clinically significant changes occurring during the study as an AE. The laboratory reports must be filed with the source documents.
- Abnormal laboratory findings associated with the underlying disease are not considered clinically significant, unless judged by the investigator to be more severe than expected for the participant's condition.
- All laboratory tests with values considered clinically significantly abnormal during participation in the study should be repeated until the values return to normal or baseline or are no longer considered significantly abnormal by the investigator or medical monitor.
 - If clinically significant values do not return to normal/baseline within a period of time judged reasonable by the investigator, the etiology should be identified and the sponsor notified.
- All protocol-required laboratory tests, as defined in Section 10.2, must be conducted in accordance with the laboratory manual and the SoA (Section 1.3).
- If laboratory values from non-protocol specified laboratory tests performed at the institution's local laboratory require a change in participant management or are considered clinically significant by the investigator (e.g., SAE or AE or dose modification), then the results must be recorded.

8.2.5. Pregnancy Testing

- Refer to Section 5.1 Inclusion Criteria for screening pregnancy criteria.
- Women of childbearing potential (WOCBP) should only be included after a confirmed menstrual period and a negative urine pregnancy test.

- Pregnancy testing will be performed at Baseline (Day 1) before study treatment administration. The urine pregnancy test at Baseline will determine study contraception and abstinence requirements as follows:
 - Pregnancy testing at Baseline (Day 1) should be performed using the urine test kit provided to the study site (with a high sensitivity of ≤ 12.5 mIU/mL). Participants with a negative urine pregnancy test result from this test kit may be included in the study with no pretreatment contraception or abstinence requirements. Women of childbearing potential are not required to be using contraception or to have practiced abstinence within 14 days prior to study entry if the high sensitivity urine pregnancy test results are negative at Baseline (Day 1).

Note: *ONLY* if the study-specific pregnancy kit provided to the study site is unavailable, a standard urine pregnancy test with a sensitivity of 25 mIU/mL may be used as an exception. A participant with a negative urine pregnancy test result from the standard test may be included in the study *only* if the participant has used a highly effective contraception method as described in Section 10.4.2 or has practiced abstinence from penile/vaginal intercourse for at least 14 days before receiving study treatment.

- After Dose 4 and before Dose 8, an additional pregnancy test using the urine test kit provided to the study site (with a sensitivity of ≤ 12.5 mIU/mL) is required to be performed for WOCBP who have not used a highly effective contraception method (in Section 10.4.2) or have not practiced abstinence from penile/vaginal intercourse for at least 14 days prior to the first dose of study treatment. It is preferable for this pregnancy test to be performed at the study site; however, for participants for whom this is not possible, the urine pregnancy kit will be provided to the participant to perform as an outpatient during the defined window. For any participant with a positive pregnancy test result, study treatment must be immediately discontinued.
- A pregnancy test will also be performed at the Test-of-Cure (Day 10 to 13) Visit, 5 to 8 days after the last dose of study treatment.
- Pregnancy testing will be performed whenever a menstrual cycle is missed or when pregnancy is otherwise suspected.
- Additional serum or urine pregnancy tests may be performed, as determined necessary by the investigator or required by local regulation, to establish the absence of pregnancy at any time during the subject's participation in the study.

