Investigator assessment of clinical response				X	X	X	The investigator will provide an assessment of clinical response (clinical success, clinical failure, or indeterminate, per the definitions in Section 10.11) for each participant at the TOC and Follow-up Visits, and at early withdrawal (if applicable). This assessment should be completed after the clinical signs and symptoms score is determined by the same study physician or otherwise appropriately medically trained staff who performed the clinical scoring assessment.
CCI							
Labs & blood/urine sampling							
Bacteriology samples	X		X	X	X	X	
 Participants will provide a clean-catch midstream urine sample at each visit for Gram stain, quantitative bacteriology culture, and in vitro antimicrobial susceptibility testing by a designated central laboratory(ies). Refer to the laboratory manual. A predose bacteriology urine sample will be collected at the On-therapy Visit.
Hematology, chemistry, and urinalysis	X		X	X			
Diagnosis of presumptive acute uncomplicated cystitis	X						Based on confirmation of nitrite or pyuria (>15 WBC/HPF or the presence of 3+/large leukocyte esterase) from a pretreatment clean-catch midstream urine sample per local laboratory procedures.
Urine pregnancy test	X		X	X		X	For women of childbearing potential, a negative high sensitivity urine pregnancy test is sufficient for eligibility. See Section 8.2.5 for Baseline urine test sensitivity requirements and 10.4 for associated contraception requirements. Pregnancy testing should

Visit	Baseline		On-Therapy ^a	TOC ^b	Follow-up	Early Withdrawal	Notes
Study Day	1		2 to 4	10 to 13	28±3	NA	be performed after Dose 4 and before Dose 8, as specified in Section 8.2.5.
Procedure	Pre-dose	Post-dose					
Serology (hepatitis B and C and HIV)	X						If serology testing was performed within 3 months prior to the first dose of study treatment and the results were positive, testing at Baseline is not required. If testing was performed within 3 months and any result was negative, testing at Baseline is required.
Drug and alcohol screen	X						
Genetic sample	X						Collect sample only if the participant has a signed consent/assent specific for this purpose. The Baseline Visit is the recommended time to collect the sample, but it can be collected at any time during the study.

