PK blood sample		X	X				
Sparse PK blood samples will be collected.
 
 At the Baseline Visit, the PK blood samples will be collected at 1-2 hours post-dose as peak concentration. At the On-therapy Visit, the PK blood samples will be collected at pre-dose as trough concentration (i.e., 12 hours post-dose, which is at the end of the dosing interval from the previous dose) and at 1-2 hours post-dose as peak concentration. 
(Further detailed information will be provided in the SRM.)

PK urine sample		X	X				
 At the Baseline Visit, samples will be collected from pre-dose to approximately 2 hours (1 to 3 hours) post-dose as pooled urine. At the On-therapy Visit, samples will be collected at pre-dose (i.e., 12 hours postdose as spot urine, which is at the end of the dosing interval from the previous dose) and from pre-dose to approximately 2 hours (1 to 3 hours) post-dose as pooled urine. 
(Further detailed information will be provided in the SRM.)

Study treatment							
Administer oral dose of study treatment		X	X				
 Participants will receive oral study treatment BID for 5 days under double-blind, double-dummy conditions. The first oral dose will be administered at the study site during the Baseline Visit; participants will self-administer as outpatients thereafter, beginning with the second dose, excluding the day of On-therapy Visit (i.e., taking morning dose at study site). Each dose should

Visit	Baseline		On-Therapy ^a	TOC ^b	Follow-up	Early Withdrawal	Notes
Study Day	1		2 to 4	10 to 13	28±3	NA	
be taken after food consumption and with water. The date and time of each dose administered at the study site will be recorded in the source documents.
 
 At the On-therapy Visit, whenever it is possible, the participant will have the pregnancy test performed at the study site. If the visit coincides with the 8th dose, the participant will take their next dose of study treatment at the study site after negative pregnancy test results are confirmed. Note: The On-therapy Visit should be scheduled to support completion of the postdose ECG within the protocol-defined window. Also, in a woman of childbearing potential, the high sensitivity pregnancy test must be performed and show negative results at the latest before Dose 8 of study treatment is taken.
Procedure	Pre-dose	Post-dose					

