6.1. Study Intervention(s) Administered

- All doses of study treatment should always be taken after food consumption and with water. Participants will receive oral study treatment (gepotidacin [2 tablets] + nitrofurantoin matching placebo [1 capsule] or nitrofurantoin [1 capsule] + gepotidacin matching placebo [2 tablets]) BID (approximately every 12 hours) for 5 days.
- The first oral dose will be administered at the study site during the Baseline Visit; participants will self-administer subsequent doses as outpatients thereafter, excluding the day of On-therapy Visit.
- At the On-therapy Visit, participants will go to the study site before taking the morning dose, have the PK sample collection performed, and then take the morning dose, while aiming to keep the time of dosing as close as possible to 12 hours after the previous evening dose was taken.
- At the On-therapy Visit, whenever it is possible, the participant will have the pregnancy test performed at the study site. If the visit coincides with the 8th dose, the participant will take their next dose of study treatment at the study site after negative pregnancy test results are confirmed.
- Before the On-therapy Visit, if the requirement for the single pregnancy test to be done between dose 4 and dose 8 cannot be done at the study site due to availability of open clinic hours and the investigator considers the participant reliable to accurately perform the study-provided pregnancy test at home will be instructed to do so. If the pregnancy test is negative, those participants will be instructed to take their next dose of study treatment at home via text or by study site staff before going to the study site for their On-therapy Visit.

Note: The On-therapy Visit should be scheduled to support completion of the postdose PK sample collection and ECG within the protocol-defined window. Also, in WOCBP, the high sensitivity pregnancy test must be performed and show negative results at the latest before Dose 8 of study treatment is taken.

Table 2 Study Intervention(s) Administered

Intervention Label	Gepotidacin	Placebo (Matched to Nitrofurantoin)	Nitrofurantoin	Placebo (Matched to Gepotidacin)
Intervention on Label	Gepotidacin (GSK2140944)	Placebo (Matched to Nitrofurantoin)	Nitrofurantoin	Placebo (Matched to Gepotidacin)
Intervention Description	Tablet for BID dosing	Capsule for BID dosing	Capsule for BID dosing	Tablet for BID dosing
Type	Drug	Drug	Drug	Drug

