- Specimens for microbiological testing will be collected, as described in Section 8.1. Clinical signs and symptoms of acute cystitis will be recorded, as described

in Section 8.1.3.1 and 10.10. **CCI** [REDACTED]

- Pregnancy testing, as required, after Dose 4 and before Dose 8. Refer to Section 8.2.5 for details.
- **TOC (Day 10 to 13) Visit:** Participants will be instructed to return to the study site 5 to 8 days after completion of study treatment in order to complete the TOC Visit. Assessments will be performed as shown in the SoA (Section 1.3), including the following:
 - The TOC Visit will be preceded by a documented reminder contact from the study site to the participant 24 ± 4 hours before the scheduled appointment time per the method (e.g., text message, telephone call, e-mail) confirmed with the study site staff prior to departing the study site on Day 1.
 - Specimens for microbiological testing will be collected, as described in Section 8.1. Clinical signs and symptoms of acute cystitis will be recorded, as described in Section 8.1.3.1 and 10.10. Investigator assessment of clinical response will be documented per the definitions described in Section 8.1.3.2 and 10.11. **CCI** [REDACTED]
- **Follow-up (Day 28±3) Visit:** Participants will be instructed to return to the study site on Day 28 (±3) in order to complete the Follow-up Visit. Assessments will be performed as shown in Section 1.3, including the following:
 - The Follow-up Visit will be preceded by a documented reminder contact from the study site to the participant 24 ± 4 hours before the scheduled appointment time per the method (e.g., text message, telephone call, e-mail) confirmed with the study site staff prior to departing the study site on Day 1.
 - Specimens for microbiological testing will be collected, as described in Section 8.1. Clinical signs and symptoms of acute cystitis will be recorded, as described in Section 8.1.3.1 and 10.10. Investigator assessment of clinical response will be documented per the definitions described in Section 8.1.3.2 and 10.11. **CCI** [REDACTED]
- Participants experiencing signs and symptoms suggestive of infection recurrence or relapse will be assessed and treated per the investigator's judgement.

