
Combined (estrogen- and progestogen-containing) hormonal contraception associated with inhibition of ovulation^c
 
 oral intravaginal (not approved in Japan as contraceptive method) transdermal (not approved in Japan as contraceptive method) injectable (not approved in Japan as contraceptive method)

Progestogen-only hormone contraception associated with inhibition of ovulation^c
 
 oral (not approved in Japan as contraceptive method) injectable (not approved in Japan as contraceptive method)

Sexual abstinence
 
 Sexual abstinence is considered a highly effective method only if defined as refraining from heterosexual intercourse during the entire period of risk associated with the study intervention. The reliability of sexual abstinence needs to be evaluated in relation to the duration of the study and the preferred and usual lifestyle of the participant

 Contraceptive use by men or women should be consistent with local regulations regarding the use of contraceptive methods for those participating in clinical studies. Failure rate of <1% per year when used consistently and correctly. Typical use failure rates differ from those when used consistently and correctly. Male condoms must be used in addition to hormonal contraception. If locally required, in accordance with Clinical Trial Facilitation Group (CTFG) guidelines, acceptable contraceptive methods are limited to those which inhibit ovulation as the primary mode of action.

Note: Periodic abstinence (calendar, sympto-thermal, post-ovulation methods), withdrawal (coitus interruptus), spermicides only, and lactational amenorrhea method (LAM) are not acceptable methods of contraception. Male condom and female condom should not be used together (due to risk of failure from friction)

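### The Dose 8 notes require a negative high-sensitivity pregnancy test in women of childbearing potential without exemption, but Protocol 8.2.5 exempts some through an ambiguous 'or', and its fallback Baseline kit does not meet inclusion criterion 4

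*Protocol*

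**What the plan says.** Three notes in the Protocol set a condition for Dose 8. In Section 6.1, "in WOCBP, the high sensitivity pregnancy test must be performed and show negative results at the latest before Dose 8". Section 8 (On-therapy Visit) repeats this, and the study-treatment row of the Schedule of Activities in Section 1.3 says that "in a woman of childbearing potential, the high sensitivity pregnancy test must be performed and show negative results at the latest before Dose 8". None of the three names a group that may skip the test.

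Section 8.2.5 defines who is tested in the window between Doses 4 and 8. The test, with the supplied kit (12.5 mIU/mL or better), "is required to be performed for WOCBP who have not used a highly effective contraception method (in Section 10.4.2) or have not practiced abstinence" for at least 14 days before the first dose.

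Two places defer to 8.2.5. The pregnancy-test row of the Schedule says testing should "be performed after Dose 4 and before Dose 8, as specified in Section 8.2.5". The On-therapy Visit list in Section 8 has "Pregnancy testing, as required, after Dose 4 and before Dose 8. Refer to Section 8.2.5 for details".

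For Baseline, 8.2.5 allows a fallback if the supplied kit is unavailable: "a standard urine pregnancy test with a sensitivity of 25 mIU/mL may be used as an exception". Entry on that kit is conditional; it is allowed "if the participant has used a highly effective contraception method as described in Section 10.4.2 or has practiced abstinence from penile/vaginal intercourse", with a 14-day minimum for the abstinence. Inclusion criterion 4 in Section 5.1 asks for a high-sensitivity urine test on Day 1 whatever the woman's contraception or abstinence history, and mentions no other kit. Sections 5 and 8 both rule out waivers.

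**The concern.** The Dose 8 test decides whether dosing may continue, so sites need one answer to who must have it. The notes and 8.2.5 give different answers, and 8.2.5 can itself be read in two ways. Two sites could treat the same woman differently in good faith, and a monitor could record a deviation against either.

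The fallback kit adds a second problem. A woman may be admitted on the less sensitive kit because she used contraception or abstained, and the same history may then exempt her from the only scheduled on-treatment test specified at 12.5 mIU/mL or better. The Test-of-Cure test comes 5 to 8 days after the last dose, too late to prevent any exposure. Her entry is also open to challenge, because criterion 4 does not provide for that kit.

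What is at stake is safety conduct. Section 2.3.1 says there are no data in pregnant women and relies on the study's pregnancy testing, citing 8.2.5, to limit fetal exposure. A measure named as the mitigation should read the same throughout.

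**Working it through.** No sample size, power or error rate is involved, and the plan gives no figure to reproduce. The check compares the texts and then applies simple logic.

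**Step 1. Who is exempt under each text.** Classify WOCBP by use of highly effective contraception other than abstinence (C) and by 14 days of abstinence before dosing (A).

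- Dose 8 notes: everyone is tested.
- 8.2.5, literal: test if (not C) or (not A), so only women with both C and A are exempt.
- 8.2.5, read as 'neither': test if (not C) and (not A), so women with C or A are exempt.
- Fallback kit: entry allowed if C or A.

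| C | A | Dose 8 notes | 8.2.5 literal | 8.2.5 as 'neither' | May enter on 25 mIU/mL kit |
|---|---|---|---|---|---|
| yes | yes | test | exempt | exempt | yes |
| yes | no | test | test | exempt | yes |
| no | yes | test | test* | exempt | yes |
| no | no | test | test | test | no |

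Exempt groups: 0 of 4 under the notes, 1 of 4 under the literal reading, 3 of 4 under 'neither'. The two readings of 8.2.5 disagree in 2 of the 4 groups.

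*Section 10.4.2 lists abstinence among the highly effective methods, but "abstinence is considered a highly effective method only if defined as refraining from heterosexual intercourse during the entire period of risk", meaning the risk from study treatment. If a woman's abstinence is taken to meet that definition, the third row also becomes exempt on the literal reading, giving 2 of 4. This overlap does not affect the 'neither' reading.

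**Step 2. Women who entered on the fallback kit.** They come from the first three rows. Under 8.2.5, 1 of these 3 groups is exempt on the literal reading (2 of 3 if abstinence counts as a method) and 3 of 3 on the 'neither' reading. On every reading, therefore, some fallback entrants could complete treatment with no scheduled test at 12.5 mIU/mL or better before or during dosing.

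**Step 3. What a positive test in the window would prevent.** The course is 10 doses of 1,500 mg on gepotidacin, or 10 × 1,500 = 15,000 mg. A positive result just after Dose 4 prevents Doses 5 to 10: 6 × 1,500 = 9,000 mg. Just before Dose 8 it prevents Doses 8 to 10: 3 × 1,500 = 4,500 mg. These amounts apply only if a test is positive, and the documents give no basis for that probability.

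**Step 4. Criterion 4 against the fallback.** Criterion 4 requires a high-sensitivity kit and sets contraception and abstinence history aside. The fallback uses a standard kit and depends on that history. A woman entered on it does not meet the criterion as worded.

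**The case against.** A reader might infer that no site can comply with all these texts. That does not follow. Section 8.2.5 says for whom the test is required, forbids it for no one, and lets the investigator add pregnancy tests at any time. A site that tests every WOCBP before Dose 8, and uses the supplied kit at Baseline, satisfies every text on any reading of 'or'. The texts set a stricter and a looser minimum, and a compliant path exists.

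The documents also point to 8.2.5 as the governing section. Criterion 4 does so for testing during and after treatment. The Schedule's pregnancy-test row does so for Baseline test sensitivity as well as for the on-treatment window, and 10.4.2 and the laboratory appendix (10.2) refer there too. The Dose 8 notes sit in scheduling text and could be read as setting a deadline only. This shows which section was probably meant to govern. It does not reconcile the wording: the unqualified note in 1.3 stands in the same Schedule as the row that defers, the one in Section 8 in the same visit description, and the 6.1 note has no pointer at all.

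A further inference would be that exempting fallback entrants is a design error. The documents do not support that either. On the 'neither' reading, the exempt groups are exactly those admissible on the fallback kit, which fits a coherent two-route scheme: a sensitive kit with a retest for women without protection, or a standard kit for women with it. The fallback condition, worded with 'has used or has practiced', favours that reading. Even so, that scheme contradicts the three notes and is not what the literal wording says.

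**Conclusion.** The inconsistency is real and is a minor safety-consistency correction. A site that follows 8.2.5 alone would give Dose 8 to women whom the notes say must first test negative, including some admitted on the 25 mIU/mL kit. A woman admitted on that kit also fails criterion 4 as worded, with no waiver available.

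The size is limited. The group counts above are logical cells, not numbers of women, and the number affected cannot be derived from the documents. A reader might infer a material fetal risk, but the documents do not support one. WOCBP enter after a confirmed menstrual period and a history review, continue any contraception they were using, are to abstain through Test-of-Cure, and are tested then and whenever a cycle is missed. The animal findings in 2.3.1 arose at clinically relevant exposure, but at maternally toxic doses and without drug-related malformations. No efficacy result, analysis population rule or sample size changes.

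The conclusion assumes only that the notes mean what they say for all WOCBP. If they were meant as a deadline for women already required to test, the notes are the text to amend.

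**What to change.** State one rule everywhere, by either route.

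(a) In 8.2.5, require the test between Doses 4 and 8 for every WOCBP, whichever kit was used at Baseline. The three Dose 8 notes then stand unchanged.

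(b) If the exemption is intended, reword 8.2.5 so that the test is required for WOCBP who have neither used a highly effective method nor abstained for the 14 days, and for every WOCBP included on the 25 mIU/mL kit. Insert *where required by Section 8.2.5* in the notes in 1.3, 6.1 and 8. The clause on the fallback kit is a policy choice rather than a matter of consistency. It leaves 0 of the 3 fallback groups exempt.

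For criterion 4, either delete the fallback exception from 8.2.5, or add a separate sentence after the criterion: *If the study kit is unavailable, the exception in Section 8.2.5 applies.* It should be a separate sentence because a phrase inserted before the words that set contraception and abstinence aside would create a new contradiction.

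The cost is a few words of text and at most one urine kit per woman now exempt. No visit is added, since the test is done at the On-therapy Visit or at home. A site that had to use the fallback kit would need a study kit by Dose 8, which at 12-hour dosing falls 7 × 12 = 84 hours after Dose 1.
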